## **12. EFFICACY ANALYSES**

The efficacy data will be summarized descriptively using the FAS and PP populations. Placebo subjects will be pooled across study parts for the final analyses. An overall summary by treatment group will be provided for each dosing period (i.e., entire and effective) defined in section 10.8 to show:

- Number and percentage of subjects who reported at least 1 attack (non-adjudicated), and total number of subject reported attacks
- Number of and percentage of subjects who reported at least 1 confirmed attack , and total number of confirmed attacks
- Number of and percentage of subjects who reported at least 1 confirmed attack that required treatment, and total number and percentage of confirmed attacks that required treatment
- Number of and percentage of subjects who reported at least 1 confirmed attack that did not require treatment, and total number and percentage of confirmed attacks that did not require treatment

Inferential comparisons of the efficacy endpoints will be performed for each BCX7353 dose vs. Placebo and for pairwise dose groups. The FAS and PP populations will be used for the comparisons of efficacy endpoints. All efficacy data collected on CRF will be listed. A separate listing will be provided for the derived efficacy endpoints.

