#### 12.1.4. Analysis of Secondary Efficacy Endpoints

The number and percentage of attack-free days will be analyzed similarly to the attack rate endpoint. The secondary efficacy endpoints including attack location, duration, symptoms of attacks, and number and percent of attacks requiring attack medication will be summarized for each treatment group.

The between-treatment comparisons for the weekly attack rate will be also be performed separately by attack location (peripheral or abdominal) using the ANCOVA model as described for the primary endpoint.

The attack onset relative to the time of last dose of study drug, discontinuations due to lack of efficacy and number of emergency room visits and/or hospitalizations will also be reported by treatment group.

AAS will be summarized descriptively by treatment group for each AAS question at attack level and at subject level. The most severe response from all confirmed attacks will be used at subject level summary. The between treatment group comparisons for the total AAS score and individual AAS question scores will be performed using an ANCOVA model. The adjusted qualifying attack rate will be included as a covariate.

The following additional efficacy analyses will also be performed:

- The attack rate in the pre and post treatment periods
- Time intervals between attacks

Time intervals between attacks will be derived as follows:

Subjects with no attack: Interval = duration of treatment or 28  
Subjects with 1 attack: Interval = the Max of the duration of (the first dose to start of the attack) or (stop of attack to the end of the dose )

Subjects with >1 attack: Interval = the duration between the stop of the first attack and start of the next attack (subjects with N attacks will have n-1 intervals)

- Time to first attack after the study medication

The time to first attack after the first study medication will be summarized descriptively and graphically using Kaplan-Meier method. The Kaplan-Meier (KM) estimate for the median, and the first and third quartiles will be determined along with approximate 95% confidence intervals. Brookmeyer-Crowley method will be used for the confidence interval calculation. Subjects who do not have an attack will be censored at the date of last dose for the KM analysis.

- Time to first attack after the last dose

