The time to first attack after the last dose will be summarized descriptively and graphically using Kaplan-Meier method. The Kaplan-Meier (KM) estimate for the median, and the first and third quartiles will be determined along with approximate 95% confidence intervals. Brookmeyer-Crowley method will be used for the confidence interval calculation. Subjects who do not have an attack will be censored at the date of last follow-up assessment for the KM analysis.

- Time to treatment

The time to treatment defined as the time from the start of an attack to the use of the first HAE medication reported in the diary will be derived for each attack and summarized by treatment, by country and site at attack level.

The time to first HAE medication will also summarized graphically using KM method. The KM estimate for the median and the first and third quartiles will be determined along with approximate 95% confidence intervals. Brookmeyer-Crowley method will be used for the confidence interval calculation. Subjects who do not take medication will be censored at end of the attack.

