14.2.3.1.1	Summary of Time intervals between Attacks	FAS/PP
14.2.3.2	Summary of AAS Categorical Response -Attack level	FAS/PP
14.2.3.3	Summary of AAS Categorical Response -Subject level (worst response for each AAS question)	FAS/PP
14.2.3.4	Summary of AAS Total Score (include AAS total and Domain Total Score)	FAS/PP
14.2.3.5	Statistical Analysis of AAS Total Score (include AAS total and Domain Total Score)	FAS/PP
14.2.3.6	Summary of Attack Duration at Subject Level – Confirmed Attacks	FAS/PP
14.2.3.7	Summary of Attack Duration of All Confirmed Attacks	FAS/PP
14.2.3.8	Summary of Attack Triggers – Confirmed Attacks	FAS/PP
14.2.3.9	Summary of Attack Symptoms – Confirmed Attacks	FAS/PP
14.2.3.10	Summary of Number of Symptoms – Confirmed Attacks	FAS/PP

Tables	Title	Population
14.2.3.11	Summary of Attack Location – Confirmed Attacks	FAS/PP
14.2.3.12	Summary of Attack Onset time from the last dose– Confirmed Attacks	FAS/PP
14.2.3.13	Summary of Administrations of Acute HAE Medications – Confirmed Attacks	FAS/PP
14.2.3.14	Number and Percentage of Attacks Requiring Additional Medical Care	FAS/PP
14.2.3.15	Summary of time to treatment –Confirmed Attacks (overall, by country and by site )	FAS/PP
14.2.3.16	Time to Treatment (KM estimates)	FAS/PP
14.2.3.17	Summary of Qualifying, Screening Attack and Post Treatment HAE attack Rate	FAS/PP
14.2.3.18	Statistical Analysis of Post Treatment HAE attack Rate	FAS/PP
14.2.3.19	Time of First Attack after the First Dose (KM estimates)	FAS/PP
14.2.3.20	Time of First Attack after Last Dose (KM estimates)	FAS/PP
14.2.4.1	Summary of AeQoL scores	FAS/PP
14.2.4.2	Statistical Analysis of AeQoL Scores	FAS/PP
14.2.4.3	Correlation among AeQoL and Attack Rate	FAS/PP
14.2.4.4	Summary of DASS Severity-Rating Index Categories	FAS/PP
14.2.4.5	Summary of DASS scores	FAS/PP
14.2.4.6	Correlation among DASS Domains and Attack Rate	FAS/PP
14.2.4.7	Correlation between AeQoL and DASS Domains	FAS/PP
14.2.5.1	Statistical Analysis of DASS Scores	FAS/PP
Pharmacokinetic Analysis		
14.2.5.2	Summary of Plasma BCX7353 Concentration	PK
14.2.5.3	Summary of Derived Plasma BCX7353 Pharmacokinetic Parameters	PK
14.2.5.4	Summary of Trough BCX7353 Concentration	PK
14.2.5.5	Assessment of Dose Proportionality based on Power Model	PK
14.2.5.6	Assessment of Dose Proportionality based on ANOVA	PK
14.2.5.7	Assessment of Steady State	PK
14.2.5.8	Number and Percent of Average Ctrough above 4xEC50 and 4xEC80	PK

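### Time to first HAE medication: censoring untreated attacks when they end can overstate the Kaplan-Meier share treated and print quartiles that do not exist

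*SAP*

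**What the plan says.** SAP 12.1.4 (Time to treatment) defines the variable per attack: "time from the start of an attack to the use of the first HAE medication reported in the diary will be derived for each attack", summarised by treatment, country and site. A second paragraph adds the survival analysis: "The time to first HAE medication will also summarized graphically using KM method". It continues: "The KM estimate for the median and the first and third quartiles will be determined along with approximate 95% confidence intervals", with Brookmeyer-Crowley intervals. The censoring rule is: "Subjects who do not take medication will be censored at end of the attack". SAP 16 lists the outputs as Table 14.2.3.16, "Time to Treatment (KM estimates", and a KM plot, Figure 14.2.1.13.

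The plan expects some attacks to go untreated. The overall summary in SAP 12 includes the "total number and percentage of confirmed attacks that did not require treatment" as well as the "total number and percentage of confirmed attacks that required treatment". SAP 12.1.4 adds that the "number and percent of attacks requiring attack medication will be summarized for each treatment group". SAP 10.8.1 derives a weekly rate of confirmed attacks requiring treatment, and Tables 14.2.1.10 and 14.2.2.10 analyse it.

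Neither document gives an expected share treated, an expected time to treatment or a duration for untreated attacks. The SAP does not say what is printed when a quartile is not reached.

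**The concern.** KM assumes that a censored observation remains at risk and would go on to have the event at the same rate as those still under observation. That fits an attack whose record is cut short. It does not fit an attack that resolved without medication, because its time to treatment will never be observed. Censoring it removes it from the denominator and redistributes its weight to later treatments.

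Two outputs can go wrong. The curve (1−KM) can rise above the true proportion of attacks treated by a given time. The quantiles read from it can be too early, or can be finite where the true quantile does not exist because too few attacks were ever treated. The study report could then show a KM share treated that contradicts its own crude percentage.

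A second question is the unit of analysis. The variable is derived per attack, but the censoring rule speaks of subjects. A subject who treats one attack and not another is not covered by that wording. If attacks are the unit, repeated attacks of one subject are correlated, and the stated intervals ignore that.

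**Working it through.** The plan states no figure for this analysis, so there is nothing to reproduce. The check compares the SAP rule with the cumulative incidence of treatment. When every attack is followed to treatment or end, cumulative incidence is simply attacks treated by time t divided by all attacks.

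**1. Direction, by hand.** Take ten attacks. Six are treated at 1, 2, 3, 4, 6 and 8 h. Four are untreated and end at 2.5, 5, 7 and 12 h.

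- KM survival after the last treatment: (9/10)(8/9)(6/7)(5/6)(3/4)(1/2) = 0.214, so 1−KM = 78.6%.
- Cumulative incidence: 6/10 = 60.0%.
- Quartiles under the SAP rule: 3, 6 and 8 h. True quartiles: 3 h, 6 h and not reached.
- If the four untreated attacks end at 72 to 120 h instead, both methods give 60.0% and a third quartile not reached.

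So 1−KM is never below cumulative incidence, and exceeds it whenever an untreated attack ends before a later treatment.

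**2. Size at 24 h.** Assumptions, none from the documents: 60% treated, treated times lognormal with median 3 h and log-SD 1.0 or 1.5, untreated durations lognormal with log-SD 0.8, 300,000 simulated attacks per case.

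| Median untreated duration | Excess of 1−KM at 24 h |
|---|---|
| 8 h | about 15–16 points (75% against 59% at log-SD 1.0) |
| 24 h | about 2–3 points (61% against 59% at log-SD 1.0) |
| 72–96 h | under 1 point |

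**3. Quantiles.** Here the assumed treated median is 6 h (log-SD 1.0), with 200,000 attacks per case.

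| Share treated | Untreated median | 1−KM at 48 h | True at 48 h | KM quantiles against truth |
|---|---|---|---|---|
| 60% | 8 h | 90.5% | 58.9% | Q3 24.0 h; does not exist |
| 60% | 24 h | 67.7% | 58.9% | Q3 117.9 h; does not exist |
| 60% | 96 h | 59.2% | 58.8% | Q3 not reached by either |
| 40% | 8 h | 78.8% | 39.3% | median 17.7 h, Q3 41.5 h; neither exists |
| 80% | 8 h | 95.7% | 78.3% | Q3 16.1 h against 28.5 h |

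**4. Realistic attack counts.** Protocol 5.3.3.3 gives an interim placebo rate of 0.898 per week and reductions of 0.384 (350 mg), 0.417 (250 mg) and 0.579 (125 mg). Over 4 weeks, attacks number 20 × 0.898 × 4 = 71.8 on placebo, 18 × 0.514 × 4 = 37.0 on 350 mg, 6 × 0.481 × 4 = 11.5 on 250 mg and 7 × 0.319 × 4 = 8.9 on 125 mg. In simulated samples of 10 to 70 attacks (true share 60–70%, assumed treated median 4 h), KM printed a third quartile although under 75% were treated in 56–99% of samples at an untreated median of 8 h, 18–59% at 24 h and 0–4% at 96 h.

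**5. Clustering, if the unit is the attack.** The design effect is 1 + (m − 1) × ICC, with m attacks per subject, and intervals are too narrow by 1 − 1/√(design effect). The ICC of 0.3 to 0.5 is assumed.

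| Arm | m | Design effect | Too narrow by |
|---|---|---|---|
| Placebo | 3.59 | 1.78–2.30 | 25–34% |
| 350 mg | 2.06 | 1.32–1.53 | 13–19% |
| 250 mg | 1.92 | 1.28–1.46 | 12–17% |
| 125 mg | 1.28 | 1.08–1.14 | 4–6% |

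**The case against.** The strongest reply is that the bias may be negligible. Protocol 5.1 says that symptoms typically subside over 3 to 5 days. If untreated attacks last that long and treatment comes within hours, the excess is under 1 point at 24 h. This stands as one end of the range. It does not settle the matter: the passage describes attacks generally, not those left untreated. SAP 10.1 also sets a missing stop date to 11:59PM on the start date, which brings some censoring forward.

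A reader might infer that the rule hides a fall in use of attack medication on active drug. The documents do not support that. The share treated is reported as a crude count and percentage, and the weekly rate of treated attacks has its own inferential tables; none of these uses the KM curve. That the bias differs between arms is plausible if the drug changes attack duration or severity, but nothing in the documents shows it.

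A reader might also infer that all intervals are about a third too narrow. The 34% is the upper end for placebo, under an assumed ICC. The KM paragraph can also be read as one record per subject, in which case the clustering point falls away.

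Finally, time to treatment is neither a listed secondary endpoint (SAP 2.2.2) nor a comparison of interest (SAP 7.2). That is correct, and it limits the weight of the point.

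**Conclusion.** The censoring rule is wrong for the quantity it estimates, and the direction of the error does not depend on any assumption. Its size does. Over the range checked at 60% treated and a treated median of 3 h, the excess at 24 h runs from under 1 point to about 16 points, depending mainly on how long untreated attacks last. A median that does not exist can be printed only if under 50% are treated, and such a third quartile only if under 75% are. The documents do not say which case applies, so it cannot be claimed that the share will be overstated materially or that false quartiles will appear. The interval point holds only if attacks are the unit. The effect is confined to Table 14.2.3.16 and Figure 14.2.1.13; the primary endpoint and the planned summaries of treated attacks are untouched. Low severity, but worth correcting.

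**What to change.** In SAP 12.1.4, replace the KM estimate with the cumulative incidence of first HAE medication, counting resolution without medication as a competing event, so that untreated attacks stay in the denominator. Report a quantile as not reached when the share treated is too low to define it. State whether the unit is the attack or the subject and reword the censoring rule to match. If it is the attack, use subject-level bootstrap intervals in place of Brookmeyer-Crowley. Retitle Table 14.2.3.16 and Figure 14.2.1.13 accordingly. The cost is SAP wording and a standard procedure. No new data are needed, and SAP 11.3 already allows computational algorithms to be refined.

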#### 12.1.4.1. Angioedema Quality of Life (AE-QoL)

The AE-QoL (Weller, Groffik et al. 2012) consists of four domains and a total score.

Dimensions	Item
Functioning	1. Impairment of work
	2. Impairment of physical activity
	3. Impairment of spare time activities
Fatigue/Mood	4. Impairment of social relations
	6. Difficulties of falling asleep
	7. Waking up during the night
	8. Feeling tired during the day
	9. Difficulties in concentrating
	10. Feeling downhearted
Fears/Shame	12. Feeling burdened at having swellings
	13. Fear of new suddenly appearing swellings

	14. Fear of increased frequency of swellings
	15. Ashamed to visit public places
	16. Embarrassed by the appearance of swellings
	17. Fear of long term negative drug effects
Nutrition	5. General limitations in foods and eating
	11. Limitations in the selection of food and beverages
Total Score	Items 1 to 17

The AE-QoL domain scores and the AE-QoL total score are calculated using the following formula:

$$(\Sigma \text{ items} - \text{min } \Sigma \text{ items}) / (\text{max } \Sigma \text{ items} - \text{min } \Sigma \text{ items}) \times 100$$

where

$\Sigma$  items= Sum of reported item scores per CRF

min  $\Sigma$  items= Sum of the Minimum possible score for each domain

max  $\Sigma$  items= Sum of the Maximum possible score for each domain

The calculated AE-QoL ranges from 0 (best) to 100 (worst).

The actual and change from baseline scores by domain and total will be summarized by visit and treatment. The AE-QoL change from baseline will be analyzed using an ANCOVA model. The estimated treatment difference for each BCX7353 dose– Placebo at each visit (ie, Baseline, and Day 29) will be displayed together with the 95% confidence interval and the associated p-value. Least Squares Means (LS Means) for each visit will also be presented with the standard error and the number of subjects contributing to the LS Means. The responses to the individual AE-QoL questions will also be listed.

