## **11.2. Subject-Completed Assessments**

### **11.2.1. Quality of Life Questionnaires**

To assess quality of life, the AE-QoL and DASS questionnaires will be administered once at Baseline, Day 14 (DASS only) and at Day 29.

For all subject-completed forms, clinic staff should ensure the subject reads the instructions and completes the questionnaires in full prior to filing in the source documentation.

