#### 12.1.4.2. Depression, Anxiety, Stress Scales (DASS)

The DASS (Crawford and Henry 2013) is a set of three self-report scales designed to measure the negative emotional states of depression, anxiety and stress. Each of the three DASS scales contains 14 items, divided into subscales of 2-5 items with similar content. The Depression scale assesses dysphoria, hopelessness, devaluation of life, self-deprecation, lack of interest/involvement, anhedonia, and inertia. The Anxiety scale assesses autonomic arousal, skeletal muscle effects, situational anxiety, and subjective experience of anxious affect. The Stress scale is sensitive to levels of chronic non-specific arousal. It assesses difficulty relaxing, nervous arousal, and being easily upset/agitated, irritable/over-reactive and impatient. Subjects are asked to use 4-point severity/frequency scales to rate the extent to which they have experienced each state over the past week. Scores for Depression, Anxiety and Stress are calculated by summing the scores for the relevant items.

The rating scale is as follows:

0 Did not apply to me at all

- 1 Applied to me to some degree, or some of the time
- 2 Applied to me to a considerable degree, or a good part of time
- 3 Applied to me very much, or most of the time

Scores of Depression, Anxiety and Stress are calculated by summing the scores for the relevant items.

The depression scale items are 3, 5, 10, 13, 16, 17, 21, 24, 26, 31, 34, 37, 38, 42.

The anxiety scale items are 2, 4, 7, 9, 15, 19, 20, 23, 25, 28, 30, 36, 40, 41.

The stress scale items are 1, 6, 8, 11, 12, 14, 18, 22, 27, 29, 32, 33, 35, 39.

The score for each of the subjects over each of the sub-scales, are then evaluated as per the severity-rating index below.

	Depression	Anxiety	Stress
Normal	0-9	0-7	0-14
Mild	10-13	8-9	15-18
Moderate	14-20	10-14	19-25
Severe	21-27	15-19	26-33
Extremely Severe	28+	20+	34+

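### As written, the AE-QoL formula scores an unanswered item as the best response or better, because it sets reported items against full-domain limits

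*SAP*

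**What the plan says.** SAP 12.1.4.1 uses one formula for the four AE-QoL domains and the total: the item sum minus the minimum sum, divided by the maximum sum minus the minimum sum, times 100. The item sum is the "Sum of reported item scores per CRF". The other two terms are the "Sum of the Minimum possible score for each domain" and the "Sum of the Maximum possible score for each domain". The result is said to run from 0 for best to 100 for worst. On the analysis the section says: "The AE-QoL change from baseline will be analyzed using an ANCOVA model". Each dose is compared with placebo, with a 95% confidence interval and a p-value.

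For DASS, SAP 12.1.4.2 says: "Scores for Depression, Anxiety and Stress are calculated by summing the scores for the relevant items". Each scale has 14 items scored 0 to 3. There is no rescaling, and the DASS text does not say that only reported items are summed.

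Neither section says how to score a questionnaire with unanswered items. Protocol 11.2.1 asks clinic staff to make sure that the subject "completes the questionnaires in full prior to filing in the source documentation".

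**The concern.** The two parts of the AE-QoL formula cover different sets of items when a form is incomplete. The numerator loses the blank item, while the minimum and maximum still count it. The visit score therefore drifts toward the good end of the scale for a reason unrelated to the subject's condition.

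Quality of life is a secondary objective (SAP 2.1.2). The scores feed the dose-placebo comparisons and also the correlations with attack rate described in SAP 12.1.4.2. The arms are small: Protocol 5.4.1.3 expects 6 subjects on 62.5 mg in Part 3. At 125 mg and 250 mg the planned ratios give about 6 in Part 2 and 6 in Part 3, so about 12 each when pooled. One incomplete form can move an arm mean noticeably in a short domain.

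**Working it through.** **Inputs.** The formula and item lists come from SAP 12.1.4.1: Nutrition has 2 items (5 and 11), Fears/Shame has 6 (12 to 17) and the total has 17. The item coding is not given. I assume five-point items and show both 0-4 and 1-5, so the range per item is 4 in each case.

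**The plan's own range first.** For k items, all answered:

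score = 100 × (sum − k × lowest) / (k × 4)

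All items at the lowest value give 0, and all at the highest give 100, under either coding. The stated 0 to 100 range is reproduced for complete forms.

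**One item blank.** The sum now has k − 1 terms, but k × lowest and k × 4 do not change. Compared with the complete form, a blank item whose true raw score is x shifts the score by −100 × x / (4k).

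- Nutrition, other item at mid-scale, 0-4: 100 × (2 − 0) / 8 = 25.0
- Nutrition, other item at mid-scale, 1-5: 100 × (3 − 2) / 8 = 12.5
- Total, other 16 items at mid-scale, 0-4: 100 × (32 − 0) / 68 = 47.1
- Total, other 16 items at mid-scale, 1-5: 100 × (48 − 17) / 68 = 45.6

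| Score | Coding | Complete, mid-scale | One blank, rest mid-scale | Lowest possible, one blank | Highest possible, one blank |
|---|---|---|---|---|---|
| Nutrition (2) | 0-4 | 50.0 | 25.0 | 0.0 | 50.0 |
| Nutrition (2) | 1-5 | 50.0 | 12.5 | −12.5 | 37.5 |
| Fears/Shame (6) | 0-4 | 50.0 | 41.7 | 0.0 | 83.3 |
| Fears/Shame (6) | 1-5 | 50.0 | 37.5 | −4.2 | 79.2 |
| Total (17) | 0-4 | 50.0 | 47.1 | 0.0 | 94.1 |
| Total (17) | 1-5 | 50.0 | 45.6 | −1.5 | 92.6 |

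Under 1-5 coding the score can leave the stated range. Under either coding, 100 can no longer be reached.

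**Change from baseline, no true change, items at mid-scale.** A Nutrition item blank at Day 29 gives 25.0 − 50.0 = −25.0 (0-4) or 12.5 − 50.0 = −37.5 (1-5), a false improvement. The same blank at baseline gives +25.0 or +37.5, a false worsening. For the total, a blank at Day 29 gives −2.9 or −4.4.

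**Effect of one such subject on an arm's mean change.** Nutrition, 6 subjects: 25.0/6 = 4.2 to 37.5/6 = 6.3 points. Nutrition, 12 subjects: 2.1 to 3.1 points. Total, 12 subjects: 2.9/12 = 0.2 to 4.4/12 = 0.4 points.

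**Does another section repair it?**

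- SAP 10.1 bases the planned analyses on reported data and considers imputation only for the primary endpoint.
- SAP 10.4 sets a change to missing when a visit value is missing. Here the formula still returns a value, so that rule does not come into play.
- SAP 10.2 excludes subjects with missing data points, but only for concentration data.
- Protocol 11.2.1 lowers the number of blanks and does not say how to score one.

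**DASS.** Fourteen Depression items scored 1 sum to 14 (Moderate). If one were blank and counted as 0, the sum would be 13 (Mild). The SAP does not say that this is how a blank is handled.

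**The case against.** The best defence is that the word reported only identifies the source, the raw values on the CRF, and that the formula was written for complete forms. The stated 0 to 100 range supports this, since a literal reading can break it. Staff check the forms at the clinic, the individual answers will be listed so blanks would be visible, and SAP 11.3 lists missing-data rules and algorithms among its possible revisions. The documents give no evidence that any items were skipped.

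Much of this stands as mitigation. It does not tell a programmer what to do with a blank, and the definitions as they stand produce the scores above. SAP 11.3 permits a later correction but does not make one.

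Three stronger readings are tempting, and the documents do not support them.

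- A reader might infer that every blank counts as an improvement. The direction of the change depends on which visit has the blank. Under 0-4 coding, a blank whose true answer is the lowest value causes no shift at all.
- A reader might infer that DASS has the same fault. Its text has no full-domain limits to mismatch and no instruction to sum only reported items. An incomplete sum could equally be set to missing, and SAP 10.4 would then set the change to missing.
- A reader might infer a bias in favour of BCX7353. Nothing in the documents suggests that blanks would differ between arms or between visits.

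**Conclusion.** The point holds for AE-QoL and is minor. Read literally, SAP 12.1.4.1 scores an unanswered item as the best response under 0-4 coding, or as one raw point better than the best under 1-5 coding, and no other section corrects this. With the other items at mid-scale, one blank costs 25 to 37.5 points in Nutrition but only 2.9 to 4.4 in the total, so the short domains carry nearly all the risk. These sizes rest on the assumed five-point coding and on mid-scale answers; the documents give neither the coding nor a rate of blank items.

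For DASS the finding is only that the plan is silent. Severity is low because quality of life is listed under other secondary endpoints (Protocol 7.2.4), the study has no formal hypotheses (Protocol 13.2.4), and completeness is checked on site.

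**What to change.** In SAP 12.1.4.1, define the minimum and maximum sums over the items answered. Add that a domain or total score is missing when more than a pre-stated share of its own items is blank. State the item coding as well. With limits over answered items, a form with one blank and the rest at mid-scale returns 50.0 in every domain and in the total, the range stays 0 to 100, and the false change is 0.

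The share has to be chosen with the domain sizes in view. A 25% limit, as an example, would make two-item Nutrition missing if either item is blank (1/2 = 50%). It would keep Fears/Shame with one blank (1/6 = 16.7%) and the total with up to four (4/17 = 23.5%). The sponsor should check the limit against the instrument publication that the SAP cites, which I have not seen.

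In SAP 12.1.4.2, add for consistency that a blank DASS item is not counted as 0, and say what is done instead.

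The cost is a few sentences and a small programming change. Complete forms score as before. The downside is that a few scores may become missing.
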